7.2.1.3. Assessment of Expectedness

The reference safety information (RSI) for this trial will be within the current IB. The sponsor will be responsible for assessment of expectedness for all AEs to determine regulatory reporting requirements. An unexpected AE is one that is not listed within the RSI of the IB.

7.3. Adverse Events and Risks

Overall, setmelanotide has been generally well-tolerated in previous trials. The most common adverse reactions have been injection site reactions, skin hyperpigmentation, nausea, headache, diarrhea, abdominal pain, back pain, fatigue, vomiting, depression, upper respiratory tract infection, and spontaneous penile erection. The investigator (or a covering clinician) will be available at all times to trial participants in the event of a clinical emergency. This availability and how to reach the investigators in an emergency will be clearly communicated orally and in writing to trial participants. All trial interventions will be provided free of cost.

Please refer to the current IB for a comprehensive summary of the AEs reported to date.

7.3.1. Medical Monitoring

The medical monitoring for the trial may be delegated to a medical monitor supplied by the Contract Research Organization (CRO) managing the operational conduct of this trial. The investigator has overall responsibility for the integrity of the trial and participant safety at their site. This information, as well as any other unanticipated problems involving risks to patients or others, will also be reported to the applicable regulatory authorities in accordance with regulatory requirements.

7.4. Monitoring of Adverse Events and Period of Observation

AEs will be recorded on the CRFs starting from V1 up to and including the patient's last visit. SAEs and deaths will be recorded on the CRFs starting from the time the ICF is signed and continuing through the patient's last visit. All AEs should be monitored until they are resolved or are clearly determined to be due to a patient's stable or chronic condition or intercurrent illness(es).

Any SAE that occurs at any time after completion of the trial, which the investigator considers to be related to study drug, must be reported to the sponsor or designee.

7.5. Guidelines for Additional Monitoring and Suspension of Dosing for a Patient

Patients will be monitored carefully during the treatment period during onsite clinic visits as well as periodic telephone calls made to the patients by the trial staff. In the event a patient is withdrawn from treatment due to an AE, the patient should be encouraged to complete the ET Visit in order to monitor the event to resolution and obtain additional protocol defined safety assessments.

Specific guidelines for dermatological events and penile erections are provided in the Appendices (Section 11, Appendix 11.2, and Appendix 11.3). At all times, this guidance is subject to the clinical judgment of the investigator and trial consultants (if applicable).

The investigator will notify the Medical Monitor in the event any trial participant fulfills any of the criteria defined in the appendices noted above, or undergoes additional monitoring for any of the events defined herein.

Male and female sexual function and hyperpigmentation will be monitored throughout the trial using specific CRF pages.

7.5.1. Depression or Suicidality

A patient should be referred to a mental health provider (MHP) if he/she has:

• Any suicidal behavior.

A referral to an MHP should also be made if in the opinion of the investigator it is necessary for the safety of the patient. Any event necessitating referral to an MHP is to be reported as an AE. If a patient's psychiatric disorder can be adequately treated with psychotherapy and/or pharmacotherapy, then the patient, at the discretion of the MHP, should be continued in the trial.

Any elevation in **Sector** should be evaluated to determine whether it meets the criteria for reporting as an AE.

8. STATISTICAL PROCEDURES

This section describes the plans for analysis. Details of the statistical analysis will be described in the Statistical Analysis Plan (SAP) and the final clinical trial report.

8.1. Sample Size Estimation

The primary objective of this trial is to evaluate long-term safety and tolerability in patients with various rare genetic, syndromic, or acquired forms of obesity impacting the MC4R pathway after completing planned setmelanotide treatment in a previously completed index protocol. All patients who complete an index protocol and meet eligibility criteria can enroll in this trial. Thus, sample size estimation and power analyses are not relevant.

Given the rarity of these genetic and acquired diseases of the MC4R pathway, estimated power for exploratory endpoints such as expected will not be provided, and efficacy will be only summarized.

8.2. Hypotheses

Setmelanotide continues to be safe and well tolerated throughout this extension protocol.

Setmelanotide leads to a clinically relevant reduction of body endpoints and longterm maintenance of weight-related improvements in each population of patients with rare genetic, syndromic, or acquired diseases of obesity (each population analyzed separately).

8.3. Definition of Population(s) for Analysis

This protocol includes a variety of patient populations who are included as a matter of administrative convenience (each population is so rare this protocol anticipates a small number of patients in each population). Each sub-population may be analyzed separately as ≥ 2 patients are enrolled, and complete at least 6 additional months of treatment.

8.4. Statistical Methods

Statistical methods, populations and approaches to missing data will be outlined in the SAP.

As these patient populations are extremely rare, efforts will be made to keep all patients in the trial, and all data collected, even if outside of visit windows, will be included in all analyses of endpoints. No missing data will be imputed, analyses will be carried out on all available data.

With respect to the exploratory endpoints, no adjustment for multiplicity will be included for the many patient populations in this trial as these different populations are included in this trial only for administrative convenience.

AEs will be coded by using the most current version of Medical Dictionary for Regulatory Activities (MedDRA) and summarized by system organ class and preferred term for the number and percent of AEs reported, the number of patients reporting each AE, and the number of patients with any AE.

Analyses of AEs will be performed for those events that are considered treatment-emergent, where treatment-emergent is defined as any AE with onset after the administration of study drug through the end of the trial, specifically, 30 days after the last dose of setmelanotide, or any event that was present at baseline but worsened in severity or was subsequently considered drug-related by the investigator through the end of the trial.

A by-patient AE data listing including onset and resolution dates, verbatim term, preferred term, treatment, severity, relationship to treatment, action taken, and outcome will be provided.

Safety data including laboratory evaluations and vital signs assessments will be summarized by time of collection. In addition, change from baseline to any post-dose values will be summarized for vital signs and clinical laboratory results. Frequency of patients with abnormal safety laboratory results will be tabulated.

Safety and efficacy data from both the index and extension trial may be combined to evaluate long-term safety and efficacy outcomes on a patient specific and population basis.

It is planned that analyses may be completed once all patients within each sub-population/cohort have completed at least 1 year of this extension protocol, data have been cleaned and finalized, and the database is locked for assessments in this first year. Additional supplemental analyses will be conducted on a yearly basis for patients who continue in the trial (for up to 7 years).

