2.2. Trial Endpoints

2.2.1. Primary Endpoint

The safety and tolerability of setmelanotide, as assessed by the frequency and severity of AEs, as well as changes in physical examinations, vital signs, laboratory evaluations, and injection site reactions.

2.2.2.

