5.4. Duration of Patient Participation

The duration of patient participation in this extension trial is up to 7 years. Patients may continue setmelanotide treatment under this protocol until they become eligible for commercially available setmelanotide, until any applicable trial cohorts are stopped, or if any AEs require treatment discontinuation. The end of the trial will be defined as the last patient's last visit. Patients may be offered the opportunity to participate in other setmelanotide clinical trials (see Section 3.4).

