5.4.1. Commercial Availability of Setmelanotide

Patient participation in this long-term extension trial will conclude once setmelanotide receives marketing authorization indicated for the patient's condition and is available for commercial use in the region. The sponsor will notify a clinical site once commercial product is available for any applicable patient.

Once this occurs and the patient has access to authorized setmelanotide, the patient will complete an ET visit in person as soon as possible. This will be considered the final trial visit for this patient. The assessments outlined in the SOA for the ET visit should be performed and the patient will return all remaining study drug to the site. A follow-up telephone call may be conducted to follow-up on any new or ongoing AEs from this final visit. This telephone call will mark the end of participation in the trial for this patient.

In the event that a patient has opted to access commercial setmelanotide treatment and is due for another trial visit prior to assuring commercial drug access, then the patient should be discussed with the sponsor. With sponsor approval, the next planned trial visit may occur as per the SOA to minimize gaps in treatment if needed.

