2. SUBJECT POPULATIONS

2.1. **Population Definitions**

• Safety Analysis Population (SAS) – The SAS includes all subjects who received at least one dose of treatment in RM-493-022. The safety population will be used for all analyses.

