3.2. General Methods

All data listings that contain an evaluation date will contain a relative study day (Rel Day). Pretreatment and on-treatment study days are numbered relative to the day of the first dose of study medication which is designated as Day 1. The preceding day is Day -1, the day before that is Day -2, etc. The last day of study medication is designated with an "L" (e.g., Day 14L). Posttreatment study days are numbered relative to the last dose and are designated as Day 1P, Day 2P, etc.

All output will be sorted and labeled according to the International Conference on Harmonisation (ICH) recommendations and formatted to the appropriate page size(s).

Tabulations will be produced for appropriate demographic, baseline, efficacy, pharmacokinetic, and safety parameters. For categorical variables, summary tabulations of the number and percentage of subjects within each category (with a category for missing data) of the parameter will be presented. For continuous variables, the number of subjects, mean, median, standard deviation (SD), minimum, and maximum values will be presented. . For the reporting of descriptive statistics, the mean and median will be reported to 1 decimal place more than the source data; the minimum and the maximum values will be presented to the same precision as the source data, and SD will be reported to 2 decimal places more than the source data.

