3.5. Methods of Pooling Data

For safety-related analyses, data will be pooled across index studies and rare genetic disorders of obesity and summarized together. For non-safety-related analyses, data will be pooled by rare genetic disorder of obesity within study, as applicable, and data will therefore be summarized by index study.

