4.5.2. Adverse Events

All AEs will be coded using the MedDRA coding system (version 25.0 or higher) and displayed in tables and in data listings using system organ class (SOC) and preferred term (PT). AE Grade assessment will be based on Investigator reporting using the National Cancer Institute Common Terminology Criteria for Adverse Events [NCI CTCAE], version 4.03.

Summarization will focus on incidence of drug product related AEs, treatment-emergent SAEs by SOC and PT,

A by-subject listing for the following AEs that occurred on extension study will also be provided: drug product-related AEs, treatment-emergent SAEs, drug product-related SAEs, deaths, AEs leading to study withdrawal, and subject deaths. Adverse event listings will be sorted by index study.

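### Adverse event frequency is planned in the readable text only as crude counts and percentages, although follow-up can run from one dose to 7 years; exposure-adjusted and by-interval rates should be added.

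*Protocol*

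**What the plan says.** **Endpoint.** Protocol 2.2.1 defines the primary endpoint as safety and tolerability, "as assessed by the frequency and severity of AEs, as well as changes in physical examinations" and in vital signs, laboratory evaluations and injection site reactions. AE frequency is one component among several.

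**AE summaries.** Under Protocol 8.4, AEs are to be "summarized by system organ class and preferred term for the number and percent of AEs reported, the number of patients reporting each AE", together with the number of patients with any AE. In SAP 4.5.2, "Summarization will focus on incidence of drug product related AEs, treatment-emergent SAEs by SOC and PT"; the sentence then breaks off after a comma. A percentage of subjects comes from the general rule for categorical data in SAP 3.2, "summary tabulations of the number and percentage of subjects within each category".

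**Pooling.** SAP 3.5: "For safety-related analyses, data will be pooled across index studies and rare genetic disorders of obesity and summarized together".

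**Follow-up.**
- Shortest: SAP 2.1, "The SAS includes all subjects who received at least one dose of treatment in RM-493-022".
- Longest: Protocol 5.4, "The duration of patient participation in this extension trial is up to 7 years".
- Commercial exit: Protocol 5.4.1, "Patient participation in this long-term extension trial will conclude once setmelanotide receives marketing authorization" for the patient's condition and the drug is available in the region.
- Other exits: termination of the MC4R cohort with exceptions for responders, AEs, non-adherence, and no evidence of benefit after a year on drug (Protocol 4.4); transfer to another setmelanotide trial, with possible return (Protocol 3.4).

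**Time information.** SAP 4.1 tabulates total time followed and SAP 4.5.1 summarises exposure. Neither is linked to the AE tables. Protocol 8.4 also plans a by-patient AE listing with onset dates and yearly supplemental analyses for patients who continue.

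**The concern.** The aim is to characterise long-term safety, so the AE tables need to show how often events occur per unit of time on drug, and whether that changes over the years. A percentage of everyone ever dosed does neither when follow-up is very unequal. A patient who leaves in the first months because the drug became available locally counts the same in the denominator as one observed for 7 years.

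Two consequences follow. First, the pooled percentage depends on the mix of follow-up lengths as well as on the event rate, so it is hard to compare with another trial, or between successive data cuts of this one. Second, a harm that starts only after several years is divided by all dosed patients, including those who left before it could appear. No AE table in the readable text is split by time on treatment, so neither late onset nor a rising frequency would be visible there.

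**Working it through.** **No figure to reproduce.** The protocol and SAP state no AE rate, follow-up distribution, sample size calculation or power. The actual distortion cannot be computed. What follows is an illustration.

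**Inputs.**
- Follow-up range: one dose to 7 years (SAP 2.1, Protocol 5.4).
- Patients by index study in SAP Table 1-1: 9 + 13 + 119 + 12 + 38 + 14 + 1 = 206.
- First-event hazard r, constant over time: assumed, 0.05 to 0.20 per patient-year.

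**Step 1: crude percentage at one true rate.** Crude percentage = 1 − exp(−r × T), with T in years.

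| r per patient-year | 1 year | 3 years | 5 years | 7 years | Ratio, 7 y to 1 y |
|---|---|---|---|---|---|
| 0.05 | 4.9% | 13.9% | 22.1% | 29.5% | 6.1 |
| 0.10 | 9.5% | 25.9% | 39.3% | 50.3% | 5.3 |
| 0.20 | 18.1% | 45.1% | 63.2% | 75.3% | 4.2 |

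**Step 2: the order can reverse.** A group with r = 0.20 followed for 1 year shows 18.1%. A group with half that rate, r = 0.10, followed for 5 years shows 39.3%. This matters if sub-populations are analysed separately, as Protocol 8.3 allows.

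**Step 3: a pooled table.** Take 206 patients, assume half are followed for 1 year and half for 5 years, with r = 0.10 throughout.
- Patients with an event: 103 × 0.0952 + 103 × 0.3935 = 9.8 + 40.5 = 50.3. The crude percentage is 50.3 / 206 = 24.4%.
- Patient-years at risk to first event or end of follow-up, each half being 103 × (1 − exp(−r × T)) / r: 98.0 + 405.3 = 503.3.
- Exposure-adjusted rate: 50.3 / 503.3 = 10.0 per 100 patient-years, the same in both halves.

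The rate recovers the assumed hazard. The 24.4% would change with the follow-up mix alone.

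**Step 4: dilution of a late event.** In the same example, an event that can occur only after year 1 can be seen in 103 patients but is divided by 206. Its crude percentage is half the percentage among those who stayed.

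**Step 5: is the planned exposure a usable denominator?** SAP 4.5.1 defines extension exposure as last dose date minus first dose date plus 1.
- No deduction is stated for time in another trial before re-entry (Protocol 3.4; note to SAP Table 1-1).
- It does not stop at the first event.
- It omits the 30 days after the last dose that Protocol 8.4 includes in the treatment-emergent window.

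Time at risk therefore has to be derived anew.

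**The case against.** **The SAP text is incomplete.** SAP 4.5.2 breaks off after a comma, and the SAP's abbreviation list defines an AE of special interest that the readable SAP never uses. Removed text could contain more. This stands: the point covers the readable text only, and a reader should not infer that an exposure-adjusted analysis is certainly absent.

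**Follow-up is not purely administrative.** A reader might infer that the design alone sets length of stay, independently of safety. Protocol 4.4 and 5.4 do not support that, since AEs end treatment, and lack of benefit and non-adherence end it too. Rates in late intervals will describe the patients who stayed, and dividing by patient-years does not remove that selection.

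**There are mitigations.** Protocol 8.4 allows a first analysis once all patients in a cohort have completed 1 year, then yearly supplements for those who continue. Follow-up and exposure are tabulated and onset dates listed. Injection site findings, laboratory values, vital signs and physical examinations are summarised by visit (SAP 4.5.3, 4.5.4, 4.5.10, 4.5.11). These help, and a rough overall rate could be formed from them. However, Protocol 8.4 does not say that the supplements split AEs by year on drug, and SAP 3.13 and 3.14 mention only data cuts and a final analysis at last subject last visit.

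**The hazard may not be constant.** Protocol Appendix 11.2 reports hyperpigmentation in the first 7 to 14 days. For such an event the crude percentage hardly changes with longer follow-up, while an overall rate per patient-year falls as follow-up lengthens. This is correct, and it is why an overall rate is not enough without the interval table.

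**The trial is single-arm and descriptive.** No decision threshold rests on an AE percentage. That limits the seriousness, but description of safety is the primary objective.

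**Conclusion.** The point holds for the readable text. AE frequency is planned only as crude counts and percentages, pooled across index studies, over follow-up that can run from one dose to 7 years. The percentages reflect length of follow-up as well as the true rate, and no AE table shown would reveal late onset or rising frequency.

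At an assumed constant hazard of 0.10 per patient-year, crude incidence runs from 9.5% at 1 year to 50.3% at 7 years. Over hazards of 0.05 to 0.20, the 7-year to 1-year ratio is 6.1 to 4.2. A reader might infer a distortion of that size in this trial. The documents do not support it: they give no rates or follow-up distribution, and the SAP pools safety data, so it does not set a 1-year group beside a 7-year group. Nor do the percentages reflect length of stay alone.

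This is a worthwhile, inexpensive improvement to a descriptive analysis, and the crude counts remain valid as counts.

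**What to change.** In SAP 4.5.2, keep the crude counts and add the following for treatment-emergent AEs, serious AEs, related AEs and AEs leading to withdrawal:

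- patients with a first event per 100 patient-years at risk;
- events per 100 patient-years;
- both overall and by 12-month interval from the first extension-study dose, with number at risk and patient-years in each interval.

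Define time at risk in the SAP. It should match the treatment-emergent window (first extension dose to 30 days after the last), be censored at the first event for first-event rates, and exclude time in another trial before re-entry. The exposure formula in SAP 4.5.1 should not serve as the denominator.

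Counting from the first extension dose keeps the analysis within SAP 3.9, which generally limits index-study data to baselines and entry characteristics. The intervals are then years in the extension, not total years on setmelanotide, and the tables should say so. If the removed part of SAP 4.5.2 already contains such rates, only the definition of time at risk and the intervals need checking.

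**Cost.** No new data collection is apparent for the basic derivation: exposure already requires dose dates, and onset dates are already listed. The work is the time-at-risk derivation, SAP wording and programming of extra tables. Late intervals will be sparse and should be read with their patient-years.

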3.4. Transition into Another Rhythm Trial

Patients enrolled in this extension trial may exit the trial to participate in other setmelanotide clinical trials with the patient's (or legal guardian's) written informed consent, at the discretion of the investigator and sponsor. The patient is to complete the extension Transition Visit prior to commencing treatment in the other setmelanotide clinical trial; applicable data from this visit will serve as Screening data for the other trial. After completion of the Transition Visit, the patient will not need to complete the Early Termination (ET) visit in the extension trial prior to transition to the other trial.

At the conclusion of the other setmelanotide trial, the patient may transition back into this extension trial, again with the patient's written informed consent, at the discretion of the investigator and sponsor, if continuation of setmelanotide treatment is considered beneficial and the patient continues to be eligible for the extension trial. In such cases, the patient will resume the extension trial at the time point/visit at which he or she was at prior to transition to the other trial. Furthermore, after transition back into this extension trial, the patient is to receive setmelanotide at the same dose as they had received prior to transition to the other trial, unless the dose needs to be reduced due to tolerability reasons or in case a dose increased is required for potential additional efficacy needs, at the investigator's discretion. If at the time the patient completes the other setmelanotide trial, setmelanotide becomes commercially available for an indication for which that patient qualifies, the patient will not be eligible to re-enter this extension trial.

If a patient transitions to another setmelanotide clinical trial before completing the ET visit in this extension trial, but does not transition back into this extension trial, the patient will not complete the ET visit or follow-up in the extension trial.

If feasible, patients are to have no interruption in setmelanotide treatment between this extension trial and the other setmelanotide trial. If an interruption in treatment is necessary due to administrative reasons, every effort is to be made to minimize the duration of the interruption and interruptions >21 days are not permissible without prior approval from the sponsor.

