7. ADVERSE EVENTS

Monitoring of adverse events (AEs) will be conducted throughout the trial. AEs will be recorded in the CRFs from V1 through the patient's last visit, as indicated in Table 1. AEs that occur after the start of study drug administration will be considered treatment-emergent adverse events. Any AEs that are reported as ongoing at the time of the subject's final visit in their index trial, will be recorded as pre-existing condition on the trial AE logs. Serious adverse events (SAEs) will be recorded through the patient's last visit. All AEs should be monitored until they are resolved or are clearly determined to be due to a patient's stable or chronic condition or intercurrent illness(es).

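### The treatment-emergent AE window runs to 30 days after the last dose, but AE recording is tied to the last visit, so coverage of the full window is not assured on every exit route

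*Protocol*

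**What the plan says.** **Analysis window.** Protocol Section 8.4 restricts the AE analyses to treatment-emergent events. It closes the window at the end of the trial, "specifically, 30 days after the last dose of setmelanotide".

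**Collection window.** Section 7 says "AEs will be recorded in the CRFs from V1 through the patient's last visit, as indicated in Table 1". Section 7.4 repeats the rule: "AEs will be recorded on the CRFs starting from V1 up to and including the patient's last visit". For serious events it says "SAEs and deaths will be recorded on the CRFs starting from the time the ICF is signed and continuing through the patient's last visit". The only later duty to report new events is narrower: "Any SAE that occurs at any time after completion of the trial, which the investigator considers to be related to study drug, must be reported".

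**Contacts after treatment.** Table 1 has a Follow-Up column after the end-of-treatment and early termination (ET) columns, with AE assessment marked. No week or day is visible for it. Footnote 26 lets the visit become a telephone call for patients who complete the trial and stay on setmelanotide, and has the site document new AEs at that call.

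**Two exit routes with their own rules.** For patients moving to commercial drug, Section 5.4.1 makes the ET visit the final trial visit and then says: "A follow-up telephone call may be conducted to follow-up on any new or ongoing AEs from this final visit". For patients who move to another setmelanotide trial before the ET visit and do not come back, Section 3.4 says "the patient will not complete the ET visit or follow-up in the extension trial".

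**SAP.** Section 4.5.2 plans summaries of treatment-emergent SAEs, but its readable text gives no window. Footnote 22 of the schedule of assessments, in both documents, gives the window a start and no end.

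**The concern.** The frequency and severity of AEs lead the primary endpoint (Protocol Section 2.2.1). The analysis rule counts days from the last dose, while the collection rule depends on a visit. If the last AE contact falls before day 30, an event can belong in the primary safety summary with no rule requiring anyone to record it. A non-serious AE, or an SAE or death judged unrelated, would be lost in this way.

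The chance of loss depends on how the patient leaves. Exit route is linked to indication and region, because authorisation is (Protocol Sections 1 and 5.4.1). SAP Section 3.5 pools safety data across index studies and disorders, so uneven capture would not show in the summary.

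**Working it through.** The plan states no figure to reproduce. The check is a comparison of the rules, followed by simple arithmetic on the one quantity the documents leave open.

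**Step 1: does any rule join the two windows?** Section 5.4 defines the end of the trial as the last patient's last visit. Section 8.4 puts it 30 days after the last dose. Sections 7 and 7.4 use the patient's last visit and give no number of days. Section 7.4 also asks for AEs to be monitored until resolved, but that covers events already recorded, not new onsets. No readable text requires collection of all AEs to day 30.

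**Step 2: what is the last AE contact on each route?**
- *Completion or withdrawal, with the Follow-Up visit attended:* the Follow-Up visit, timing not stated.
- *Completion while staying on setmelanotide:* the Follow-Up visit or a call in its place (footnote 26), timing not stated.
- *Move to commercial drug (Section 5.4.1):* the ET visit, where remaining study drug is returned. A call afterwards is optional and undated. Footnote 26 cites Section 5.4.1 yet reads as if one contact takes place, so the two do not agree.
- *Move to another setmelanotide trial without return (Section 3.4):* the Transition Visit, which has AE assessment marked. Nothing follows in this trial.

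**Step 3: how much of the window can be uncovered?** Let d be the days from the last dose to the last AE contact. The documents do not give d, so it is varied as an assumption.

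Uncovered days = max(0, 30 − d); share of the window = uncovered days / 30.

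- d = 0: 30 days, 100%
- d = 7: 23 days, 77%
- d = 14: 16 days, 53%
- d = 21: 9 days, 30%
- d = 28: 2 days, 7%
- d = 30 or more: 0 days, 0%

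**Step 4: how many patients?** SAP Table 1-1 sums to 9 + 13 + 119 + 12 + 38 + 14 + 1 = 206. The POMC/PCSK1, LEPR and BBS/AS index trials supply 13 + 12 + 38 = 63 (63/206 = 30.6%). This does not count the commercial route. Authorisation is regional, Protocol Section 1 does not list Alström syndrome as approved, and the trials labelled only as genetic disorder of obesity may include approved indications. The note to Table 1-1 shows that transfers to another setmelanotide trial (RM-493-037) have occurred, but gives no number who did not return.

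**Step 5: is a rate affected?** Protocol Section 8.4 plans numbers and percentages, and SAP Section 4.5.2 plans incidence. SAP Section 4.5.1 calculates extension exposure as last dose date minus first dose date + 1, with no 30-day tail. No person-time denominator in the readable plan includes these days.

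**The case against.** The strongest reply is that no shortfall is shown. Section 7 refers to Table 1, Table 1 marks AE assessment at Follow-Up, and that contact is then the last visit. If it falls on day 30 or later, there is no gap. Footnote 26 lets the mode of contact vary but still has new AEs documented. Other collection exists too. Footnote 2 allows AEs to be gathered by telephone from patients who withdraw, Section 4.4 follows skin AEs for up to about 90 days where feasible, and related SAEs remain reportable after the trial. The two routes without an assured contact mostly involve patients who stay on setmelanotide, so theirs is not a plain off-drug tail. Redacted text may also hold the timing of the Follow-Up contact or a window in SAP 4.5.2.

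Much of this stands. A reader might infer that the last 30 days go uncollected for many patients; the documents support no such count. A reader might also multiply 206 patients by 30 days (206 × 30 / 365.25 = 16.9 patient-years) and call that lost risk time. That assumes every patient has left with no contact after the last dose, and it measures a quantity that no readable analysis uses.

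The mismatch between the rules survives. An undated contact does not guarantee day 30, an optional call guarantees nothing, and Section 3.4 rules follow-up out. Nor does continued treatment elsewhere settle the matter. Section 8.4 counts from the last dose of setmelanotide without saying whether this means study drug, so the end of the window is undefined for those patients. Section 3.4 also allows interruptions of up to 21 days without prior sponsor approval, so a real off-drug gap can occur.

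**Conclusion.** The point holds as one of assurance: the stated rules do not guarantee that AEs are collected over the whole window in which they are to be counted. The uncovered part ranges from 0 to 30 days per patient according to an unstated contact time. Collection to day 30 is least secure for patients who move to commercial drug and for those who enter another setmelanotide trial and do not return.

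The likely effect is some under-counting of AEs that varies with exit route. Its size cannot be derived, because neither the contact time nor the number leaving by each route is given. No planned rate is biased through its denominator. The conclusion rests on the readable text; a redacted Follow-Up time of 30 days or more would close the gap for patients who have that contact, but not for the other two routes. It is worth correcting because it concerns the primary endpoint and the remedy is cheap.

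**What to change.** - **Protocol Sections 7 and 7.4:** end AE and SAE recording, including deaths, at the later of the last visit and 30 days after the last study dose in this trial.
- **Table 1:** give the Follow-Up contact a time point that matches.
- **Section 5.4.1 and footnote 26:** reconcile them by changing the call in 5.4.1 from one that may take place to one that will.
- **Section 3.4:** provide for patients who do not return, for example by carrying over AEs recorded in the next trial through the linked patient number described in Section 4.3.
- **SAP 4.5.2:** state one treatment-emergent window, anchored to the last study dose in this trial, and align Section 8.4 and footnote 22 with it. Flag events that start after a switch to commercial drug or another setmelanotide trial, so that they can be read separately without being dropped.

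The cost is wording in both documents plus one telephone call per leaving patient, which the protocol already foresees. No dose or treatment rule changes.
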